2. The research assistant (RA) will guide the participants to complete a packet of survey questions. The questionnaires will ask about demographics, co-morbidities, physical activity (self-reported), *social participation*, their perception of the influence of contextual environment (physical and social environment) on daily lives, and potential barriers and facilitators of diabetes care.
3. The RA will direct the participants to complete a standardized education module, where they will learn to use the wrist-worn accelerometer to rate their response to pre-determined questions using a numerical

rating scale and entering responses, and to record addition information on activities and /or barriers or facilitators to PA in an accompanying logbook. [name] group has already refined this education module to teach older veterans with osteoarthritis and low back pain to use a similar accelerometer and logbook to obtain data on PA and symptoms. We will adapt [name] education module for this study. The accelerometers are designed for assessment of PA patterns over time and will be worn by each participant in their home environment for 7 continuous days (allowing capture of data on both weekdays and weekends). At five pre-determined times throughout the day, the accelerometers will prompt the participants to enter responses to 3 pre-determined questions to assess their perception of the contextual environment on their ability to participate in PA and social activities (i.e., momentary assessment of the environment). Based on experience by [name] group, we will set the accelerometer alarm at wake up time, 11am, 3pm, 7pm, and before bedtime. Time for waking up and going to bed will be individualized for each participant. Each participant will know when their accelerometer alarm will go off. This will help the participant to pay attention to the alarm.

- Participants will become familiar with an accompanying logbook, in which participants will record the exact environment and activities they were involved in at two-hour intervals (See Appendix for the mock Activity Log). The logbook provides supplementary data that are important for the tailoring intervention, and also serves to cross-validate the items entered in the accelerometer. The logbook will be used as a back-up if there are missing data from the accelerometer.

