Hypothesis 2a: *At the end of 6 months, individuals in the intervention group will have increased PA compared to the control group.* PA is measured in 3 ways using Actiwatch and CHAMPS (Table 5), so three separate analyses will be done using each measure – Actiwatch daily average counts and weekly counts, and CHAMPS weekly measurement.

The primary analysis is based on comparing the 6-month change in PA between treatment group and control group by t-tests. To adjust for potential confounding, separate models of multivariate regression analyses will be conducted with each measure of PA as the dependent variable, randomization arm as a predictor, baseline PA as a covariate, and potential confounders including age, sex, diabetes status, and number and perception of environment barriers will be included in the model. Assuming that residuals from the model fit are normally distributed, the analysis is equivalent to a classical analysis of covariance. For data that does not fit a normal distribution, inverse, logarithmic or power transformations will be performed or generalized linear models (GLM) with Poisson or gamma error will be considered.

To further assess if the pattern of PA changed, i.e., whether the change in PA occurred across each day or just a few days in a week, we will graphically compare the daily average counts at 6-month follow-up for the intervention group with the control group (Figure 5). For example: If Y_{ij} = daily average counts at day_j over 7 days after intervention for subject i and j = 1 (d1), 2 (d2), ..., 7(d7), then we will try to fit the linear mixed model to test if the slopes of the two PA curves are the same and test for overall difference ($\beta_1 = 0$):

$$Y_{ij} = \beta_0 + \beta_1 * \text{intervention} + \beta_2 * \text{days} + \beta_3 * z + \epsilon_{ij}$$

With this small sample of 28-35 participants per treatment group, it is possible that the study may be underpowered to determine significant differences between groups. However, the results will provide essential information about the actual effect size of the treatment which will allow us to better estimate the sample size needed for a larger trial.

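### The exploratory daily-pattern test compares straight-line slopes over d1 to d7, which cannot tell an every-day change in physical activity from a few-days change

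*Combined protocol and SAP*

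**What the plan says.** The place is the combined protocol and SAP, Statistical Analysis, Hypothesis 2a, the paragraph on the pattern of PA that follows the primary t-tests and the adjusted regressions.

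- **Question.** It asks "whether the change in PA occurred across each day or just a few days in a week".
- **First method, a plot.** The plan states: "we will graphically compare the daily average counts at 6-month follow-up for the intervention group with the control group" (Figure 5, which is not reproduced in the text available).
- **Second method, a model.** Offered as an example that the team will try to fit, it is a linear mixed model to "test if the slopes of the two PA curves are the same and test for overall difference", the latter being β₁ = 0. The outcome is described as "daily average counts at day_j over 7 days after intervention for subject i", with j running from 1 (d1) to 7 (d7).
- **Printed equation.** It has an intercept, one intervention term, one linear term in days, an undefined covariate z and a residual. It has no intervention-by-days term, no weekday term and no written subject effect.

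Under Research Procedures, Baseline data collection, the accelerometer is worn for "7 continuous days (allowing capture of data on both weekdays and weekends". No start weekday is fixed. At baseline, wear simply follows the visit. The documents do not say whether d1 means the first wear day or a fixed day of the calendar week.

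**The concern.** A straight-line slope measures steady drift from d1 to d7. The question is about something else: whether the arm effect sits on all days or on some. If quite different day patterns give the same slope difference, the only formal test of pattern in this paragraph does not bear on the question it is meant to answer.

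The printed equation also lacks the intervention-by-days term, so as written it forces equal slopes. Adding that term would make the announced test possible, but it would still compare two straight lines.

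At stake is what the pilot learns about how the intervention works. The counselling is tailored to particular routines (the worked example in the intervention section is one hour of inactivity on a Monday), so change on only a few days is plausible. The paper is also explicit that the results are to inform a larger trial.

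**Working it through.** **Inputs.** From the documents: seven days j = 1 to 7; one linear day term; 28 to 35 participants per arm. No effect size, SD, alpha or power is stated for this analysis, so there is no figure of the plan's to reproduce. Assumed here: two-sided alpha 0.05; an effect δ of 0.5 to 1.0 within-person day-to-day SD (σ); intraclass correlation (ICC) 0.3 to 0.7. The slope results in steps 1 and 2 need none of these assumptions.

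**Step 1: what the slope comparison measures.** The mean of 1 to 7 is 4, and Σ(j−4)² = 9+4+1+0+1+4+9 = 28. With δ_j the arm effect on day j,

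slope difference = Σ(j−4)δ_j / 28.

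- Equal effect on all seven days: δ × 0/28 = 0.
- Effect on d4 only: 0 × δ/28 = 0.
- Effect on d1 and d7: (−3+3)δ/28 = 0.
- Effect on d3 and d5: (−1+1)δ/28 = 0.

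Equal slopes therefore fit both answers. A non-zero slope does not identify the days either: an effect δ on d6 and d7 gives (2+3)δ/28 = 0.179δ, and so does an effect of (5/3)δ on d7 alone.

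**Step 2: weekend-only effect if d1 is the first wear day.**

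| Start day | Weekend falls on | Slope difference | Share of between-day effect variation on the line |
|---|---|---|---|
| Monday | d6, d7 | +0.179δ | 62.5% |
| Tuesday | d5, d6 | +0.107δ | 22.5% |
| Wednesday | d4, d5 | +0.036δ | 2.5% |
| Thursday | d3, d4 | −0.036δ | 2.5% |
| Friday | d2, d3 | −0.107δ | 22.5% |
| Saturday | d1, d2 | −0.179δ | 62.5% |
| Sunday | d1, d7 | 0 | 0% |

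The seven values sum to 0, so an even mix of start days averages to 0.

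**Step 3: power of the slope test, once the interaction is added.** The standard error of the slope difference is σ√(2/(28n)).

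- n = 35, δ = 1.0σ, Monday start: 0.179/0.0452 = 3.95, power about 98%. Thursday start: 0.0357/0.0452 = 0.79, about 12%. Sunday start or even mix: 5%.
- n = 28, δ = 0.5σ: 5% to 42% across start days.

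A simulation of 2,000 runs (n = 35, δ = 1σ, ICC 0.5) rejected in 5.4% for a Sunday start, 5.1% for mixed starts and 97.7% for a Monday start. For a uniform effect it rejected in 5.5%.

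**Step 4: the overall test.** β₁ averages over the week and sees 2δ/7 = 0.286δ. At n = 35 and δ = 1σ its power is 35%, 20% and 12% for ICC 0.3, 0.5 and 0.7. It cannot tell a two-day effect of δ from a uniform effect of 0.286δ.

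**Step 5: day of week as a factor.** For an effect on any two fixed calendar days, the noncentrality is (n/2)(δ/σ)²(2 − 4/7) = (n/2)(δ/σ)²(10/7), whichever days they are. At δ = 0.5σ the joint 6-df test has power 33% (n = 28) and 41% (n = 35). At δ = 1.0σ it has about 94% and 98%.

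**The case against.** **The plot comes first.** A reader might infer that the plan has no means of seeing single days. That is not so: the plot is the leading method, and the model is an illustration. This stands, and it confines the point to the formal test. The plot is nevertheless descriptive, and if drawn by wear day with mixed starts it would blur any effect tied to calendar days.

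**The meaning of d1 is not stated.** A reader might infer that a weekend effect would be missed outright. That requires d1 to be wear day with Sunday or evenly mixed starts. With a Monday start, or with d1 defined as Monday, the slope test does respond to a weekend effect, and β₁ sees a diluted effect under any reading. Step 1 holds under either definition.

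**No decision rule is given.** The documents do not say that equal slopes will be reported as a uniform change. A wrong conclusion is therefore a risk and not something the plan commits to.

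**Using only the 6-month week is not itself a fault.** In a randomized comparison, the arm difference on each day at 6 months estimates the effect on that day. Baseline data would add precision and show within-person change.

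**A weekend contrast is no general cure.** The plan never hypothesises a weekend effect. With total SD 1, ICC 0.5 and an effect of 0.5, the standard error of an arm-by-weekend contrast at 28 per arm is √(2 × 0.5 × 0.7/28) = 0.158. Power at 28 and 35 per arm is 87% and 94% when the effect is on the weekend (z = 0.5/0.158 = 3.16 at 28). For two fixed weekdays it is 24% and 29% (contrast 2 × 0.5/5 = 0.2 in size, z = 1.26 at 28). For Saturday plus two weekdays it is 6% at either size. This stands and shapes the fix.

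**Conclusion.** The point holds for the formal test in an exploratory analysis. Whatever d1 means, a comparison of straight-line slopes cannot separate an every-day effect from a few-days effect, because both can give a slope difference of exactly zero. That is algebra and rests on no assumption.

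How badly the test does against a weekend effect depends on facts the documents leave open: about 5% power if d1 is wear day and starts are evenly mixed, rising to about 98% with a uniform Monday or Saturday start, 35 per arm and an assumed effect of one within-person day SD. Even then, a tilt does not show which days changed.

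A reader might infer that the efficacy conclusions are compromised. They are not: the primary t-tests on 6-month change and the adjusted regressions do not use this model. It is worth correcting because the test misses its own question and the correction is cheap.

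**What to change.** In the pattern paragraph of Hypothesis 2a:

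1. State what d1 is, and replace the linear day term with calendar day of week as a categorical factor. Derive it from the recorded date, which Data Management lists as an item in each record.
2. Include arm, day and arm-by-day terms, a subject random intercept, and the participant's baseline daily mean as covariate. This also supplies the interaction missing from the printed equation.
3. Test arm-by-day jointly (6 df) and report the arm difference with a confidence interval for each day.
4. Draw Figure 5 by calendar day.
5. If wanted, prespecify a 1-df arm-by-weekend contrast as secondary. It should not be the only test, since it is weak or blind for days outside the weekend.

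A per-person count of days above the baseline mean should not be used to separate the patterns, because it rises under both.

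**Cost.** SAP wording and one derived variable from data already collected. There are 6 − 1 = 5 more interaction degrees of freedom, so less power against a truly linear trend, and only modest power at 28 to 35 per arm (33% to 41% for a 0.5σ effect on two days). Single-day intervals will be wide: at ICC 0.5 and without baseline adjustment, the half-width is 1.96 × √(4/28) = 0.74σ at 28 per arm.

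**A limit that remains.** If each participant changes on two days of their own and these are spread evenly over the week, every calendar day shows the same average effect of 2δ/7. The day-of-week factor then looks uniform too, and the report should say so.

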Hypothesis 2b: At the end of 6 months, individuals in the intervention group will have improved social participation (ability to participate and satisfaction with participation). Social participation will be measured with the PROMIS questionnaires with a population mean of 50 and standard deviation of 10. The change in *social participation* will be compared between the treatment and control groups by t-tests, similar to the analysis plan described for *Hypothesis 2a*. Multivariate regression analyses will be conducted to evaluate confounding factors, with social participation as the dependent variable, randomization arm as a predictor, baseline social participation as a covariate. Potential confounders including age, sex, co-morbidities, and number and perception of environment barriers will be included in the model. Distribution of the residuals from model fit will be examined, and additional transformations and generalized linear models will be considered.

Additional analyses:

Further exploration of effects at each time points are of interest. Models will utilize outcome measurements at all time-points (baseline, 5 weeks, and 6 months). Different outcome measures and covariates can be evaluated. Repeated measure longitudinal models can be considered:

For example: **Outcome at 5 weeks and 6 months = BA + G + CF + G*TIME + CF*TIME,**

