where BA=outcome at baseline; G=intervention group; CF= one or more contributing factors; TIME= time variable; *=interaction between variables. The key aspects of this model for hypotheses 2a and 2b are interactions G*TIME and CF*TIME, and the magnitude and significance of these interaction effects provide insight into mechanisms underlying study group differences. The remaining terms are used to reflect study design and adjust for baseline values. This analysis will yield three tests: 1) a test for outcome changes over time of the study, 2) a test of the intervention vs. control group differences (an intervention effect), and 3) a test for interaction of intervention effect with time. As in the primary hypothesis, we are primarily interested in the overall intervention effect. However, a changing intervention effect over time, as reflected in intervention by time interaction is of great interest since it might suggest that the intervention has a greater impact as time progresses, which would provide support for long-term effect of the intervention. The following methods will be considered: linear mixed effects (LME) models for continuous variables with normally distributed residuals; and generalized linear models (GLM). Both of these methods allow for unbalanced data, time-varying covariates, and structured covariance matrices. Repeated measures models will be developed in the framework of linear mixed effects (LME) models or generalized linear mixed effects models (GLMM).

AIM 3: To assess participant satisfaction with the intervention, we will use a series of Likert scale satisfaction items and a semi-structured interview protocol including open-ended questions to obtain feedbacks. A quantitative analysis and a qualitative analysis will be performed for this aim:

- Results from the Likert scale satisfaction items will be analyzed to identify the association between different characteristics of the study participants and their satisfaction with the intervention. Participant characteristics (e.g., age, sex, race, education background, functional status, co-morbidities, etc.) will be cross-tabulated with the satisfaction outcomes, which can be dichotomized into satisfied or not satisfied. Individual relationships will be assessed using χ^2 tests. Multiple logistic analyses will be used to analyze responses according to each factor, controlling for socio-demographic variables.

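### As printed, two exploratory model equations lack a term needed for a test the plan assigns to them: TIME in the repeated-measures example, intervention-by-days in the daily model

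*Combined protocol and SAP*

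**What the plan says.** **Repeated-measures example (Statistical Analysis, Additional analyses).** The models are optional: "Repeated measure longitudinal models can be considered". The example is "Outcome at 5 weeks and 6 months = BA + G + CF + G*TIME + CF*TIME", where BA is the baseline outcome, G the intervention group and CF one or more contributing factors. The notation is defined as "TIME= time variable; *=interaction between variables". The text then assigns tests to the model: "This analysis will yield three tests: 1) a test for outcome changes over time of the study", followed by the between-group difference and the interaction of the intervention effect with time. It also states: "The key aspects of this model for hypotheses 2a and 2b are interactions G*TIME and CF*TIME". An intervention effect that changes over time would be taken as support for a long-term effect.

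**Daily-pattern model (Statistical Analysis, Hypothesis 2a).** The question is "whether the change in PA occurred across each day or just a few days in a week". The outcome is "daily average counts at day_j over 7 days after intervention for subject i", at the 6-month follow-up. The plan says "we will try to fit the linear mixed model to test if the slopes of the two PA curves are the same" and also gives a test of overall difference, beta_1 = 0. The printed right-hand side is beta_0 + beta_1 × intervention + beta_2 × days + beta_3 × z + error. The available text does not define z.

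**The concern.** In each case the text names a test for which the printed equation has no parameter.

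In the repeated-measures example, the asterisk is defined as interaction alone, so G*TIME cannot be read as shorthand that brings in the TIME main effect. Nothing printed carries the test of change over time. The terms the plan calls central then have no fixed meaning. Under one coding, movement common to both arms between 5 weeks and 6 months appears as a growing intervention effect. Under another, it appears as a contributing factor acting over time, which the plan would read as a mechanism.

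In the daily model, a single coefficient for days forces the two arms' lines to be parallel. Equality of slopes is then assumed and cannot be tested.

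**Working it through.** The plan states no power, alpha or effect figure for either model, so there is none to reproduce. The check is on model terms, followed by an illustration of size.

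**(a) Inputs.** The model terms and the 28–35 per arm come from the plan. Assumed, because the plan gives neither: a drift δ of 0.2 or 0.5 SD, the same in both arms, between 5 weeks and 6 months; a correlation ρ of 0.5 or 0.7 between those two visits; and a two-sided 5% test. There is no true interaction.

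**What each coding makes of G*TIME.** Let D be the 6-month minus the 5-week value. Terms without TIME cancel from D, leaving γG + κCF.

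- *0/1 arm, CF absent or centred.* The model-implied change is 0 in controls and γ in the intervention arm. If both arms drift by δ, γ estimates δ when the between-arm difference in change is 0. With TIME added, the changes are τ and τ + γ, and γ estimates 0.
- *−0.5/+0.5 arm, centred CF.* The changes are −γ/2 and +γ/2. Minimising (δ + γ/2)² + (δ − γ/2)² gives γ = 0. There is no inflation (simulated 2–5%), but change over time still has no term.
- *0/1 arm, uncentred continuous CF.* With age assumed at mean 69 and SD 6, CF is nearly constant and stands in for the missing TIME, with κ close to δ/69. G*TIME stays near 5%, but age*TIME is falsely significant in 18–31% (δ = 0.2) and 73–96% (δ = 0.5) of simulated trials.
- *Class-coded arm and TIME, CF continuous or absent.* G*TIME holds one time change per arm. With age as CF, the design has rank 5 without G*TIME and 7 with it, so the default test has 2 df and mixes time with interaction (simulated 24–46% and 91–99.8%). The valid 1-df between-arm contrast can still be extracted.
- *Class-coded arm, TIME and a class-coded CF such as sex.* CF*TIME already spans TIME. The rank goes from 6 to 7, so G*TIME has 1 df and is the valid between-arm contrast (simulated 4.6–5.5%).

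**Size in the first case.** The estimate of γ is the intervention-arm mean of D, with expected standardised value λ = δ√n / √(2(1−ρ)). The controls' unmodelled drift raises the residual variance from 2(1−ρ) to about 2(1−ρ) + δ²/2, so the critical value, about 2.0, is multiplied by k = √(1 + δ²/(4(1−ρ))). The rejection rate is approximately P(Z > 2.0k − λ).

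| n per arm, ρ | δ | λ | k | Approximate rate | Simulated, as printed |
|---|---|---|---|---|---|
| 28, 0.5 | 0.2 | 0.2×5.29/1.00 = 1.06 | 1.01 | 17% | 17.3% |
| 35, 0.7 | 0.2 | 0.2×5.92/0.775 = 1.53 | 1.02 | 31% | 32.8% |
| 28, 0.5 | 0.5 | 0.5×5.29/1.00 = 2.65 | 1.06 | 70% | 70.7% |
| 35, 0.7 | 0.5 | 0.5×5.92/0.775 = 3.82 | 1.10 | 95% | 94.6% |

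The simulated column uses 10,000 replicates per cell. Separate simulations put the ranges at about 16–33% and 69–95%, agreeing to within a point or two. With TIME added, the rate is about 5% throughout.

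**(b) Daily model.** With z a subject-level covariate, the printed columns (intercept, intervention, days, z) have rank 4. Adding intervention × days raises it to 5, so the product is not already contained in the model. The implied arm difference is beta_1 on every day: the equation supports the overall-difference test and not the equal-slopes test.

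Adding the product changes what beta_1 means. Take an arm difference of 0.5 SD on days 6 and 7 only:

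- average difference = (0.5 + 0.5)/7 = 0.14 SD;
- fitted slope of the difference = (2×0.5 + 3×0.5)/28 = 0.089 SD per day;
- beta_1 with uncentred days = 0.143 − 4×0.0893 = −0.21 SD, the fitted difference at day 0.

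With days centred at 4, beta_1 is again the 7-day average, +0.14 SD.

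**The case against.** The strongest reply on (a) is that the equation is labelled an example and is shorthand, printing no intercept, error or random effect. An analyst who reads on to the three promised tests would have to fit TIME, and the plan commits to statistical guidance for Aim 2. That stands to this extent: a dropped term is the likely explanation, and the high rejection rates describe the equation applied literally. It is also right that the inflation depends on coding. With −0.5/+0.5 arm coding and a centred CF, or with class-coded arm, TIME and a factor such as sex, G*TIME is not inflated. But the plan states no coding, and under the effect coding the time test still has no term.

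On (b), a parallel-lines model is the ordinary choice for testing beta_1 once slopes have been judged equal, and the equation directly follows the mention of that test. The figure cited there is not shown in the available copy, and z could have been meant as the product. Nothing in the text says so, however, and no other equation is given for the slope comparison.

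A reader might infer that the trial's efficacy conclusions are exposed to these error rates. The documents do not support that. The primary comparisons under Hypotheses 2a and 2b are t-tests on change, supported by baseline-adjusted regressions, and neither uses these equations.

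**Conclusion.** The point holds as a minor specification error in two exploratory models. The repeated-measures example has no TIME term for a test it is said to yield, and the meaning of G*TIME depends on unstated coding. The daily model cannot test equal slopes unless z is the missing product.

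The false-positive rates of about 16–33% and 69–95% apply only to 0/1 arm coding with CF absent or centred, and rest on assumed drifts of 0.2 and 0.5 SD and assumed correlations of 0.5–0.7. They illustrate what literal use could do and do not predict this trial's error rate. It would go too far to say that G*TIME is invalid under any coding, or that class coding always gives a mixed 2-df test: that happens only when CF is continuous or absent. The absence of the two terms from the printed equations needs no assumption.

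**What to change.** **Repeated-measures example.** Print BA + G + TIME + CF + G*TIME + CF*TIME, state the coding of arm and TIME, say which term or contrast carries each of the three tests, and test G*TIME as the 1-df between-arm contrast. Centre CF only together with adding TIME: under the printed equation with a 0/1 arm, centring is what moves shared drift onto G*TIME.

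**Daily model.** Add an intervention-by-days term and test its coefficient for equal slopes. Define z. Centre days, or define the overall difference as the 7-day average, so that the beta_1 test keeps its meaning.

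**Cost.** Two rewritten equations, 1 df for each added term, and no new data. The primary analyses and the sample size stay as they are.

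### In the optional repeated-measures model, `CF*TIME` cannot explain why the arms differ when CF is a baseline factor

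*Combined protocol and SAP*

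**What the plan says.** The Additional analyses part of the Statistical Analysis section introduces the model as an option: "Repeated measure longitudinal models can be considered". The example is "Outcome at 5 weeks and 6 months = BA + G + CF + G*TIME + CF*TIME", with the terms defined as "BA=outcome at baseline; G=intervention group; CF= one or more contributing factors; TIME= time variable; *=interaction between variables".

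The text then says "The key aspects of this model for hypotheses 2a and 2b are interactions G*TIME and CF*TIME", and that "the magnitude and significance of these interaction effects provide insight into mechanisms underlying study group differences". Everything else in the model is given a supporting role: "The remaining terms are used to reflect study design and adjust for baseline values".

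Three tests are listed: change over time, intervention against control, and "3) a test for interaction of intervention effect with time". None involves CF and arm together. Elsewhere (Hypotheses 2a and 2b, Secondary analyses) such factors enter only as adjustment covariates. No arm-by-factor test and no mediation analysis is planned anywhere.

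**The concern.** The sentence gives one interpretation to two different terms. `G*TIME` contains the randomised arm, so it can describe how the arm difference develops between visits. `CF*TIME` does not contain the arm. A reader who follows the sentence would take a large or significant `CF*TIME` as a clue to why the arms differ, and a null one as a sign that the factor is irrelevant to the treatment effect. For a factor fixed at baseline, neither inference follows.

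What is at stake is the exploratory account the pilot would give of its results. The intervention is built around barriers in the contextual environment, so whether its effect varies with those barriers is a natural question. The term singled out as informative cannot answer it.

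**Working it through.** **Inputs.** From the plan: the model formula and definitions above; two modelled follow-ups (5 weeks, 6 months) with baseline as covariate; 70 participants in total, so 70/2 = 35 per arm; 28 to 35 per arm under Hypothesis 2a, where 28/35 = 0.80 would correspond to 20% loss. The plan gives no effect size, SD or alpha for this model, so there is no figure of its own to reproduce. A TIME main effect is not printed in the formula. It is included below, and it changes nothing on this point.

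**1. Algebra.** Let t = 0 at 5 weeks and 1 at 6 months, with CF fixed at baseline:

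E(Y) = b0 + bB·BA + bG·G + bC·CF + bT·t + bGT·G·t + bCT·CF·t

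- Arm difference at CF = c and time t: bG + bGT·t. The value c has dropped out, so the model imposes one arm difference at all levels of CF.
- Change from week 5 to month 6: bT + bGT·G + bCT·c. So bCT is the slope of change on CF, held common to both arms.

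With equal arms and the same spread of CF in each, the fitted bCT is about (sI + sC)/2, where sI and sC are the slopes of change on CF in the intervention and control arms.

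**2. Two cell-mean examples (assumed effects).**

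- Stable moderator: the effect is 0.6 SD with few barriers and 0 with many, the same at both visits, and nobody changes between visits. All slopes of change are 0, so `CF*TIME` = 0. With a 50/50 factor the model reports (0.6 + 0)/2 = 0.3 SD for everyone.
- Pure prognostic factor: high-barrier people lose 0.3 SD between visits in both arms, low-barrier people do not change, and the intervention does nothing. `CF*TIME` = -0.3 - 0 = -0.3, while the arm difference is 0 throughout.

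**3. Simulation.** There were 5,000 runs per scenario at 28 and 35 per arm. Assumptions not in the plan: standard normal baseline CF, slope 0.5 SD per SD of CF, within-person residual correlation 0.5, two-sided alpha 0.05. With two follow-ups, `CF*TIME` was tested by regressing within-person change on arm and CF. Ranges run from 28 to 35 per arm.

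| How CF acts | Mean `CF*TIME` | `CF*TIME` significant | Arm-by-factor term significant |
|---|---|---|---|
| Equally in both arms, 6 months only | 0.50 | 94–97% | `G*CF*TIME` 5.2–5.5% |
| Opposite directions by arm, 6 months only | 0.00 | about 8% | `G*CF*TIME` 93–97% |
| Intervention arm only, 6 months only | 0.25 | 41–49% | `G*CF*TIME` 42–52% |
| Intervention arm only, both visits | 0.00 | about 5% | `G*CF` 53–62% |
| Opposite directions by arm, both visits | 0.00 | 5–6% | `G*CF` 97–99% |

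The first row is the false lead. The second, fourth and fifth are moderators that `CF*TIME` does not show. The third is the half-size case, (0.5 + 0)/2 = 0.25, which looks the same as a weaker effect common to both arms.

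**4. Precision of `G*CF` at one visit.** With a 50/50 factor there are four cells of n/2 people. With residual SD 1, half-width = t(0.975) × sqrt(4/(n/2)).

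- n = 35: sqrt(4/17.5) = 0.478; × 1.997 (66 df) = 0.95 SD.
- n = 28: sqrt(4/14) = 0.535; × 2.007 (52 df) = 1.07 SD.

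Averaging both visits with within-person correlation 0.5 multiplies these by sqrt((1 + 0.5)/2) = 0.866, giving about 0.83 and 0.93 SD.

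**The case against.** The strongest reply is that this is an illustration. The model is optional and sits under further exploration, CF is left open, and none of the three listed tests concerns CF. The sentence also covers `G*TIME`, for which it is sound. All of this stands, and it keeps the point minor. It does not rescue the stated reading of `CF*TIME`, which the plan itself calls a key term.

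A second reply is that CF might vary over time. The plan says the methods allow time-varying covariates, and Table 3 shows the depression scale and functional status measured again at follow-up. If the intervention shifts such a factor, the overall arm difference at time t includes (shift in CF) × (bC + bCT·t), so `CF*TIME` does enter it. The algebra above is therefore limited to baseline factors. The environment measures are among these, being collected at baseline. Even for a repeated factor, `CF*TIME` alone is not the mediated effect, and the plan describes no mediation analysis.

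Third, `G*CF` tests moderation, not mechanism, and would be imprecise. This is also true. For the 0.6 SD example, power at one visit by normal approximation is about 24% at 35 per arm (0.6/0.478 = 1.26; 1.26 - 1.96 = -0.70) and 20% at 28 per arm (0.6/0.535 = 1.12; 1.12 - 1.96 = -0.84).

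A reader might also infer that the pilot would choose the wrong factors for tailoring. The documents do not support that. Tailoring is individual, from each person's baseline activity pattern, momentary ratings and logbook, and Aim 3 assigns refinement of the intervention to interviews and satisfaction items. Nor does it follow that every real moderator would be missed: the third row of the table shows one that is picked up but cannot be attributed to an arm.

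**Conclusion.** The point holds for a CF fixed at baseline. In the printed model `CF*TIME` is a prognostic course pooled over arms, and its size or significance says nothing about why the arms differ. The algebra needs no assumed effect size. The simulated percentages and the half-widths do depend on the stated assumptions and only illustrate the scale.

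The consequence is confined to the interpretation of an optional exploratory model. The primary t-tests and adjusted regressions for Hypotheses 2a and 2b are untouched, and no documented tailoring decision rests on this term. It is a low-priority correction, worth making because the wording as it stands would license a wrong conclusion.

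**What to change.** Limit the sentence on mechanisms to `G*TIME`, and describe `CF*TIME` as the prognostic course associated with the factor in both arms, not as an explanation of arm differences.

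If the investigators want to say whether the effect differs by a factor, name one or two baseline factors in advance (for example, the number of MQE barriers) and add `G*CF`, with `G*CF*TIME` if the moderation may change between visits. Report the estimates with 95% confidence intervals as exploratory effect modification, not as mechanism.

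The cost is a change of wording and one or two extra model terms per factor, on data already being collected. The downside is wide intervals, so a null interaction should not be read as evidence that the effect is uniform.
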